Specifically, Veterans will be scheduled with a staff member (someone obtaining the consent the Veteran and witness) to further discuss involvement in the project and possibly consent (based on Veteran interest). Before consent is obtained over the phone the Veteran will be mailed or electronically sent a consent form to follow along and sign. Then a research staff member would go over the consent on the phone with the participant (as written in the phone script/consent form submitted with this amendment). Please see check boxes Yes/No throughout. No procedures will take place until the verbal informed consent has been obtained with the two witnesses. Additionally, participants will be given the opportunity to do assessments over the phone (for which their data will be entered into a VA secure redcap directly) or via mail where only study PID will be on the paperwork. No names of identifiable information will be on mailed assessment packets.

(2) Subject's expectation of privacy, comfort in the research setting, comfort with research procedures: **Once a Veteran consents to participate in the study, we shall first screen them to determine eligibility. We are only enrolling Veterans who regularly receive services from or work at the JJP VAMC, so the environmental experience will not differ from their usual routine.**

b. Data Use (Please also submit a completed Research Data Inventory Form): **As [name] is a VA WOC, information they receive is not being shared outside of the VA. As [name] is a VA Employee, information they receive is not being shared outside of the VA. [name] will only receive some deidentified data and will not interact with participants or have access to PHI.**

Is data shared with external parties?

YES	X	NO	
-----	---	----	--

If Yes, answer the following. If No, proceed to question 20.c.

Is there a Memo of Understanding with the external facility?

PENDING		EXECUTED		NO	X
---------	--	----------	--	----	---

Is there a Data Use Agreement?

PENDING		EXECUTED		NO	X
---------	--	----------	--	----	---

Indicate any other data agreements:

PENDING		EXECUTED		N/A	X
---------	--	----------	--	-----	---

c. Signature and Date:

Are subjects incompetent or do they lack decision making capacity?

YES		NO	X
-----	--	----	---

If Yes, is there a signature line on the HIPAA authorization for the person legally authorized in writing by the individual or the individual's legal guardian?

YES		NO	
-----	--	----	--

d. HIPAA Waiver:

Is a HIPAA waiver being requested? **Note: we have a HIPPA waiver for the consenting process but not for the entire study.**

YES		NO	X
-----	--	----	---

If No, proceed to 20e.

(a) Is there a written plan to destroy identifiers at the earliest opportunity consistent with conduct of the research?

YES		NO	
-----	--	----	--

e. Specimens:

Are you collecting specimens (Blood, saliva, tissue, etc.) in this study?

YES		NO	X
-----	--	----	---

Will you send specimens off site for analyses? (Material Transfer Agreement may be required, unless a CRADA is executed – see the AO for research, [name])

YES		NO	X
-----	--	----	---

If yes, please indicate how transporting specimens (hand-delivered by courier, fedex,etc) who will transport and list name of institution, address and contact information for person(s) in charge of receiving, storing and processing of specimens at external site. Please also indicate how long specimens will be stored (for specimen storing), if all specimens will be used up or whether or not unused specimens will be destroyed, when they be destroyed, remaining specimens shipped back to PI at a later date, keep specimens stored indefinitely, whether or not specimens will be shared with other researchers (for specimen banking), for future analyses, etc. **NA**

If NOT sending specimens off site, please list procedure for storage here at JJPVAMC, handling, by whom, destroying, length of time storing and whether or not specimens will be used for future research. **NA**

Does the study documentation state when specimens will be labeled with identifiable or de-identified information? **NA**

YES		NO	
-----	--	----	--

f. De-Identification of Data:

Does the protocol indicate whether or not data will be de-identified?

YES	X	NO	
-----	---	----	--

If so, please indicate all that apply. If no, proceed to question 20.g.

De-identified information is provided to PI (who has access to IIHI) by his/her research team per a HIPAA authorization or waiver of authorization.	X
De-identified information is provided by PI (who has access to IIHI) to his/her research team per a HIPAA authorization or waiver of authorization.	X
De-identified information is to be sent to non-VA research team member, such as a statistician.	X
De-identified information will be disclosed to a non-VA party. If so, please identify:	

Check all that apply:

De-identified – Data does not contain any identifiers that could link the data to a specific participant. (See VHA Handbook 1605.01, Appendix B, para 2b, for a list of identifiers

that must be removed before data can be considered de-identified. Data must be de-identified in accordance with HIPAA and Common Rule criteria. Scrambling of names and social security numbers is not considered de-identified information.

Identified – Data contains direct identifiers sufficient to identify participants as indicated in VHA Handbook 1605.01, Appendix B, para 2b.

Coded – Data linked to a specific subject by a code rather than a direct identifier. While the data may contain some protected health information only someone possessing the code can link the data to a particular participant.

If coded data is checked , specify how the link or code will be maintained, and list each person/role who will have access to the link or code:

g. VA sensitive data:

(a) Is VASI shared with parties external to JJP?

YES	NO	X
-----	----	---

If Yes, is a Data Use Agreement (DUA) in place for this activity? (NOTE: See the Privacy Officer regarding DUA's.)

YES	NO	
-----	----	--

(b) Have all research staff who will transport, transmit, download, and/or store VA sensitive information (all formats and media, see VHA Handbook 1200.12, Definitions) outside of the VA protected environment obtained written approval from their immediate supervisor and JJP ISO (see the ISO for form "Authorization to Transport and Utilize VA Sensitive Information Outside Protected Environments")?

YES	NO	
-----	----	--

If yes, please name individuals who have received authorization:

(c) Collected or stored in hard copy outside of the James J Peters VAMC:

YES	NO	X
-----	----	---

If Yes, how will it be protected?

(d) Stored on non-VA computers or non-VA electronic media outside or inside the James J Peters VAMC:

YES	NO	X
-----	----	---

If YES TO ANY OF THE FOUR PRECEDING QUESTIONS, answer i-ii below:

i. Are VA sensitive data in hard copy shared with parties specified in the consent form?

YES	NO	
-----	----	--

Are documents sent with a chain of custody (registered mail, FEDEX, UPS) or hand carried?

YES	NO	
-----	----	--

If Yes, please specify:

ii. Is VA sensitive data sharing/transmission with parties specified in the consent form FIPS 140-2 compliant using encryption provided by VA (IRM)?

Transferred using data storage media (e.g., CD, USB flash "thumb" drive):

YES		NO	
------------	--	-----------	--

If Yes, please specify type of media:

Transferred using electronic data transfer (e.g., email with PKI):

YES		NO	
------------	--	-----------	--

If Yes, please specify type of electronic data transfer:

h. Protection of Media Stored at Alternate Site:

Will VA Sensitive Information be removed from the VA Protected Environment?

YES		NO	
------------	--	-----------	--

Does the study team plan to store VA sensitive information outside the VA protected environment?

YES		NO	X
------------	--	-----------	----------

If Yes, by what method it will be protected?

i. Data Repositories:

Is any data collected for this study to be shared with any other research study?

YES		NO	X
------------	--	-----------	----------

Does this study use data that is collected under a separate research study?

YES		NO	X
------------	--	-----------	----------

If Yes, provide Protocol #: MIRB #: or non-VA entity.

NOTE: If Yes for either question, please complete items a-d below for Data Research Repositories. See R&D Committee Procedures Manual, IRB SOP, and VHA Handbook 1200.12 regarding compliance with VA Research Data Repository requirements.

(a) If the repository received data, what were the sources of data being added to the research repository and the protocol(s) under which they were collected?

(b) If the repository shared data, what were the type of data released to others for use, the protocol(s) under which they were used, and the planned disposition of the data once the protocol is terminated?

(c) Were there any events involving risk to subjects or others, such as a breach of privacy or confidentiality?

(d) Were there any findings linking a negative impact on the health status of individuals in the data repository with identified causal factors, including whether there may be a clinical intervention?

21. Information Security:

a. Software:

Will specially obtained software be used?

YES	X	NO	
------------	----------	-----------	--

If Yes, please identify: SpeechExec Pro

Source of the software **JJPVA IT**

Will a license be required? **No**

How will a license be funded? **NA**

What data will be stored in temporary files on computer hard drives? **Audio recordings of the PLF sessions. Then it will be moved into a study specific shared drive**

immediately upon download. Our team is currently working on this software request with [name] and IT services ([contact]).

We purchased the Speech Exec Pro CD and dropped it off for him to install. It is approved by the VA (as [name] noted) so it's just a matter of having it installed. Then the recorder can be hooked up to the computer directly and the recording saved to a study shared folder solely for study staff. VA Webex will now also be used to record the PLF groups and the Qualitative Interview. These recordings save directly to VA Webex behind the VA firewall.

b. Web applications: (used for such purposes as recruiting subjects, completing questionnaires or processing data)

YES	x	NO	
-----	---	----	--

If Yes, please identify: VA RedCap and VA Webex

Web application's security features: Security features of Redcap can be found following this link <https://www.iths.org/wp-content/uploads/About-REDCap-Vanderbilt.pdf>. The VA-specific REDCap and VA Webex will only be used on VA computers and all the files will be de-identified. VA REDCap and VA Webex is only accessible within the VA firewall.

c. Incident Reporting:

Are procedures in place, in accordance with VA policy, for reporting incidents, i.e. theft or loss of data or storage media, unauthorized access of sensitive data or storage devices or non-compliance with security controls?

YES	x	NO	
-----	---	----	--

If Yes, please describe the procedures, and briefly describe how they are conveyed to research staff. **The research staff should report to the PI, who will then report to the proper authorities.**

DATA:

a. Data Flow:

Describe the data collection, data flow and/or data management process that will be used for the study: **Hard copy data is secured by the research coordinator and filed in locked cabinets in a locked office. Data that is entered electronically is stored on VA-secured server. No one outside of the research staff has access to these files. A password protected spreadsheet will link research ID number with patient identification, stored on the VA-secured server. Only the PI and research assistants will have access to this linkage file.**

b. Data Security Plan:

Will Electronic Data be stored?

YES	x	NO	
-----	---	----	--

If Yes, please explain how it will be secured: **All electronic data is stored on VA-secured server. Any data entered on VA Recap will be De-Identified.**

Will Paper records be stored?

YES	x	NO	
-----	---	----	--

If Yes, please explain how it will be secured: **Hard copy data is secured in locked file cabinets in the research office.**

c. Data on a Hard Drive:

Will VA research data be stored on a computer other than the VA network?

YES	NO	X
------------	-----------	----------

If Yes, will it be encrypted?

YES	NO	
------------	-----------	--

If Yes, will data that is stored outside the VA network be backed up regularly and securely stored on the VA network?

YES	NO	
------------	-----------	--

d. Storage Location:

\r04brxnas21.v03.med.va.gov\groups\MIRECC\[name]\GOO-18-18 PLF RCT

Identify location (facility, room number) where hard copy data will be stored: **9B-70**

e. Data Transmission:

Will sensitive electronic information be transmitted? (Note: VA sensitive data or information may only be transmitted using VA-approved solutions such as FIPS 140-2 validated encryption)

YES	NO	X
------------	-----------	----------

If Yes, please provide the method of transmission:

f. Data Backup:

Will original electronic VA research data stored on a mobile device be backed up regularly and stored securely within VA's protected environment?

YES	NO	N/A	X
------------	-----------	------------	----------

Will original electronic VA research data stored outside the VA protected environment be backed up regularly and stored securely within VA's protected environment?

YES	NO	N/A	X
------------	-----------	------------	----------

g. Shipping Data:

Will hard copy, electronic research data, or any encrypted media be sent via delivery service with a chain of custody?

YES	NO	X	N/A	
------------	-----------	----------	------------	--

If Yes, please describe chain of custody:

The answer is currently no, but at some point we may amend this as it is the backup option. Currently those reviewing the tapes are being WOC-ed and given remote access. This way they can be added to the study protocol through the IRB and given direct access (through remote access) to the study shared drive. If needed, we would update our protocol to include a chain of custody (registered mail, FEDEX, UPS) in which the DVD recordings would be broken after the WOCs listen to the sessions. However, we would put in an amendment and get approval before pursuing this option. Any data that will be shared will be De-Identified and shared via Fedex. The only data sent offsite will be De-Identified DVD recordings of sessions that will be broken once listened to for adherence.

Is sensitive electronic research data that must be sent via common carrier (e.g., USPS, UPS, Fedex) encrypted with FIPS 140-2 validated encryption?

YES	NO	X	N/A	
------------	-----------	----------	------------	--

h. Data Return (If no data is sent offsite, enter x here and proceed to i.):

What VA information will be returned to the VA?
How will the information be returned to the VA?

i. Termination of Data Access:

Will access to research study data be removed for study personnel when they are no longer part of the research team?

YES	X	NO	
-----	---	----	--

j. Per CRADO memo "Creation of Research Data Inventory to resolve OIG report 11-01823-294" of January 15, 2015, please submit a "Research Data Inventory Tool" to accompany this application. This tool may be found on the Research intranet page under Other Forms.

Is a form being submitted with this application?

YES		NO	X
-----	--	----	---

EQUIPMENT:

a. Will any portable, mobile or wireless devices be used for research purposes?

YES	X	NO	
-----	---	----	--

If No, proceed to Question m.

If Yes, are all these devices encrypted?

YES	X	NO	
-----	---	----	--

How are these devices backed up? **N/A Working with IRM to get it installed in the software mentioned above. Recordings would immediately be deleted off of the recorder**

Is the encryption FIPS 140-2 validated (required)?

YES	X	NO	
-----	---	----	--

Has the investigator's immediate supervisor and the CIO authorized use of any such devices (contact the CIO for procedures)?

YES	X	NO	
-----	---	----	--

b. Has all equipment owned by an affiliated institution, or purchased by such institution from grant funds, and used by the Investigator in this research project at JJP, been reported to the CIO (reporting to include: Type of equipment, Manufacturer, Model, Serial Number, PO Number, Vendor, Asset Value, Acquisition Date, Researcher's Service, and Location (Room Number)?

YES	X	NO	
-----	---	----	--

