Title: Group ("Project Life Force") vs. Individual Suicide Safety Planning RCT

NCT Number: **NCT03653637**

Date Approved: **08/03/2024**

B. PROTOCOL SUMMARY

1. Provide a brief (200-250 word) summary of background information for physician/scientists. List total # of subjects approved for enrollment by the IRB.
List total number of subjects enrolled (Signed a consent form) over the life of this study. List total number of subjects enrolled(Signed a consent form) in the current approval period. List total number of subjects terminated from study (Lost to follow-up, terminated by PI, withdrew consent, etc.). List total number of subjects that have completed all study tasks/procedures and follow-up visits. List total number of subjects currently receiving study treatment or participating in study activities.:

At present, we are unaware of any empirically supported, manualized outpatient group treatments for suicidal individuals other than a published account of a 1-session inpatient safety planning group and description of an outpatient process oriented group of variable session length and duration. Dialectical Behavior Therapy (DBT) offers a group component in its comprehensive approach, but discussion of suicidal urges, thoughts and behaviors is discouraged in the group setting. The paucity of published literature on group approaches for suicidal individuals is surprising given the numerous advantages of group treatment that include: 1) diminishing social isolation and increasing social support, a protective factor against suicide; 2) it's cost effectiveness and maximizing staff time; 3) the peer movement among those who have experienced suicidal crises is strong and growing; and 4) Veterans and military service members are used to working with a team approach to problems.

PLF is one of the first outpatient manualized suicide prevention group intervention to date. The proposed study has direct VA and military relevance as psychotherapy groups are a standard treatment modality in both settings.

2. State the purpose of the study:

The study proposes to conduct a randomized clinical trial (RCT) of a group safety planning intervention, “PLF” versus individual safety planning in 180 suicidal Veterans. Compared with the comparison condition- individual safety planning, the current standard of care, designated as treatment as usual (TAU), the PLF group will show a decrease in suicidal ideation.

3. Background of Study Population - Clinical Information:

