- a. Describe the general population from which you plan to recruit subjects for this study (i.e., Demographics of potential subjects):

Male and female Veterans from the JJP VA Medical Center will be recruited, ranging in ages from 18-89. Participants should represent the spectrum of ethnicities and races, as well as socioeconomic status of the Greater New York area. We will also be working with other IRBs at other VAs in the US to recruit but the participants will be enrolled at JJPVA

- b. Describe the medical condition in this population:

Veterans will have a history of suicidal ideation and suicide attempts (actual, aborted, or interrupted).

- c. How does this condition affect this population (symptoms)?

Models of suicidality stress the role of social factors in development and intensification of suicidal thoughts and behavior, including: feeling like a burden on family and friends feelings of isolation and not belonging (perceptions of diminished support from family/social network).

d. Does this population have an understanding or knowledge of the medical condition being studied?

Yes, this population will have at least a general understanding of the condition of suicidality.

e. What is the traditional treatment provided for this condition?

Behavioral psychotherapy, couple's therapy, and general safety planning with clinician.

f. Explain how special needs that may arise with this population due to this medical condition are addressed (e.g. Additional care provided, supportive therapy, physiotherapy, behavioral therapy): **Special needs that may arise will be addressed through contacting resident providers and support staff equipped to treat Veterans with suicidal symptoms.**

g. Describe how research subjects will be referred for appropriate care while they are enrolled in the study?

Research staff will inform subjects of appropriate care based on the subject's experience and on the research staff's own clinical judgment of the subject's wellbeing while enrolled. Examples include research staff informing subjects about enrolling in mental health services (i.e., psychiatrist, and psychosocial workers, Suicide Prevention Coordinators), providing information on the Rapid Access Clinic, and other resources such as substance abuse treatment and housing assistance that are available to all subjects.

h. Describe whether providers (all clinical staff) have experience in providing care to subjects:

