The PI ([name]) has extensive clinical and research experience with high risk suicidal Veterans, including the development of a DBT Clinical Program in VISN 3 since 2002, that now includes 7 sites across New York and New Jersey and is PI on two Department of Defense (DoD)-funded studies. The DoD research involves implementing a four-year RCT (with 18-month follow-up) of DBT for suicidal Veterans.

i. Does the James J. Peters VAMC have the appropriate medical or psychosocial resources required for any emergency needs for research subjects?

Yes.

4. Selection of subjects:

a. Indicate number of subjects to be enrolled at this site (**Total # of subjects approved by IRB**):

180

b. Indicate total number of subjects to be enrolled, if multisite study:

320

c. Are veterans being enrolled at this site?

YES	X	NO	
------------	----------	-----------	--

d. Are non-veterans being enrolled at this site?

YES		NO	X
------------	--	-----------	----------

If no, proceed to question 4.f.

Justify why non-veterans will be enrolled at this site: **NA**

Of all subjects to be enrolled at this site, what percentage will be non-veterans? **NA**

e. Describe the setting in which the research will be conducted (e.g., research office, clinic, lab, inpatient unit, outpatient unit):

Recruitment will take place via referrals from suicide prevention coordinators and [name], the attending of the inpatient unit; We will also be working with other IRBs at other VAs in the US to recruit but the participants will be enrolled at JJPVA. assessments will be done in the privacy of a research office. The group sessions will be held in a clinic room on hospital wings 3B or 6A. However, during the time of COVID-19 when groups are no longer happening in person at the hospital, group sessions will be held through telehealth (e.g., VVC and VA WEBEX with VANTS line as a backup).

f. What is the expected length of time a study subject will participate? (i.e., number of days, weeks, months, years)

12-14 months

5. Indicate the characteristics of study population (with the letter x in the appropriate column):

a. Gender:

	YES	NO
Male	X	
Female	X	

b. Age range: from _____ to _____ [max age is 89 years]

c. Racial and Ethnic/Minority Groups:

	YES	NO
Caucasian	X	
Alaskan Native	X	
American Indian	X	
Hispanic	X	
Black	X	
Asian/Pacific Islander	X	

Other: (Specify)

d. Justify any exclusion of specific gender, age, and racial or ethnic groups:

NA

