All data will be de-identified before it is entered into a redcap database at the JJPVA, Philadelphia VA, Northport VA, and Central Texas VA over the intranet. All principal analyses will be conducted based on the intention-to-treat principle. Linear mixed models will be used to examine changes in primary and secondary outcomes for Veterans over time and to examine whether the effects of PLF and TAU on these outcomes vary with time adjusted for the time-dependent treatment, covariates of interest and imbalanced baseline prognostic factors, using data reduction methods as appropriate. *For the PLF subjects, individual's random effect will be nested within the group they are assigned to, while for TAU subjects, they will be nested within the clinician effect.* All data will be entered into an SPSS database at the JJPVA constructed by the data manager. Tenets of our data system include double data entry, range checks and exclusion of identifiers that can be directly traced to individuals. Preliminary analyses will include computing descriptive statistics and inspecting features and patterns of data to determine whether data transformations are needed. Quantitative measures will be graphed and their distribution inspected for any outlier value, which will be winsorized. All principal analyses will be conducted based on the intent-to-treat principle, that is, all Veterans with data will be included, regardless of the actual treatment received. For subjects who drop out during the study, their data up to that point will be used, but not carried forward to subsequent time points. We will also conduct an economic cost analysis of the Project Life Force intervention to compare cost effectiveness of telehealth groups versus the in-person groups pre-COVID. We will use an implementation science framework, The Consolidated Framework for Implementation Research, to determine barriers and facilitators of the telehealth-delivered PLF safety planning intervention. Development of the script and qualitative analysis will be conducted by [name]; a qualitative and implementation expert.

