For the survival analysis comparing the PLF and TAU treatment conditions, we assumed a 20% dropout in both groups based on previous safety planning data to date using SAFE-VET, exponential hazard functions, and considered four scenarios of suicide behavior reduction of PLF over TAU. We assumed a base rate of 49% for SB in the TAU group based on published data from ED-SAFE. The sample sizes needed for 80% power were calculated using the “Proc Power” procedure from SAS software © 2002- 2012. In the absence of pilot data, we used a published formula for the Variance Inflation Factor from the weighted log-rank test, to adjust the required sample size for within-group, and within-clinician, dependence. We assumed m=5 subjects per group or clinician, and an ICC for suicidal behavior within the group of r=0.01 based on literature. While power analyses were calculated for several reduction rates, we selected the 35% reduction rate as the most reasonable estimation for the reasons outlined below. The composite suicide behavior outcome has minimal data outside of ED-SAFE’s reduction of 18% in non-veterans recruited from an emergency room. Stanley and Brown’s SAFEVET data on Veterans presenting to an ED, reported a 45% reduction in suicide attempts (however the composite definition of suicidal behavior was not used). Moreover we anticipate PLF to have increased potency over SAFEVET due to the group setting and greater number of in-person sessions. Balancing the enhanced potency of the PLF intervention with the new composite definition of SB, the 35% reduction scenario is reasonable. Therefore, we expect the reduction to be above the minimum values indicated, and are confident that N=145 will provide ample power for this aim. Then, the research team included an additionally 35 to be consented who would likely not screen into the study or meet inclusion/exclusion criteria.

18. Community-based Participatory Research

Is this research based on Community-based participation?

YES		NO	X
------------	--	-----------	----------

If Yes, answer questions (a-h). If No, proceed to Question 19.

a. Describe the community that will be involved in this research:

b. What is the role of the community in this research?

c. Does this research include a community organization that is engaged in research?

YES		NO	
------------	--	-----------	--

If Yes, does that organization have a Federal Wide Assurance (FWA)?

YES		NO	
------------	--	-----------	--

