Title: **Group ("Project Life Force") vs. Individual Suicide Safety Planning RCT**

NCT Number: **NCT03653637**

Date: **05/12/2025**

Primary Statistical Analysis Plan

The primary outcome of suicidal behavior will be analyzed using a Cox Proportional Hazard Regression, with treatment condition (PLF+TAU vs. TAU) and baseline suicidal behavior level as predictors, and incidence and time to the first suicidal behavior during the study course as the outcome variables. The model will adjust for treatment site. Kaplan-Meier estimates of the cumulative hazard function for both groups will be graphed and the proportionality assumption checked. If the hazard functions are not proportional, the non-parametric log-rank test will be used instead, with treatment condition as predictor, and we will use a sensitivity analysis to test the effect of baseline suicidal behavior severity by splitting the treatment conditions by the presence/absence suicidal behavior.

Most secondary and other outcomes (depression, hopelessness, thwarted belongingness, aggression dimensions, insomnia and suicide-related coping) will be analyzed in Linear Mixed Effects (LME) regression models. All LMEs will be adjusted for site and will include randomization condition, time, and a randomization by time interaction. The treatment effect of PLF+TAU vs TAU will be the treatment by time interaction. Time will be treated as a linear variable. Mixed-effect models can be fit to data with dropout or missing values as long as the data is missing at random, thus, attrition does not necessarily reduce the number of participants included in these analyses.

For the two outcomes (drug and alcohol use) that are only measured at the one-year follow-up (with retrospective questions about the past 12 months), we will compare between PLF+TAU and TAU with t-tests or Mann-Whitney U tests where appropriate.

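### The protocol gives trial sizes that cannot be reconciled (180 consents at one VA, or 320 across several), and the sample-size section supports only the smaller

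*Protocol*

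**What the plan says.** **For a 180-consent trial at JJPVA**

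- Protocol item 2 (purpose): an RCT of the group intervention (PLF) "versus individual safety planning in 180 suicidal Veterans".
- Item 4.a: 180 for this site.
- Item 11 (recruitment): opens with 180 Veterans and runs until an unnumbered target has been consented and enrolled.
- Section 17.b: settles on N = 145 and continues, "Then, the research team included an additionally 35 to be consented who would likely not screen into the study". That gives 145 + 35 = 180.
- Items 3.a, 4.e and 11: "We will also be working with other IRBs at other VAs in the US to recruit but the participants will be enrolled at JJPVA".
- Item 20.a(2): "We are only enrolling Veterans who regularly receive services from or work at the JJP VAMC".

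**For a larger, multisite trial**

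- Item 4.b: the prompt "Indicate total number of subjects to be enrolled, if multisite study" is answered 320.
- Section 17.a: data go into a "redcap database at the JJPVA, Philadelphia VA, Northport VA, and Central Texas VA", which is four VAs.
- SAP, on the primary Cox model: "The model will adjust for treatment site". The mixed models are also adjusted for site. Neither term is defined.

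**The concern.** Items 4.a and 4.b could both be true if read alone: 180 here and 320 overall. They cannot both stand beside an RCT of 180, enrolment only at JJPVA, a population limited to people who use or work at JJPVA, and a power section that ends at 180. The other 140 have no enrolling site, no derivation and no place in the power calculation.

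Sample size is a figure that the trial relies on. The sentence that ends recruitment carries no number of its own and does not separate consented from randomised. A reader therefore cannot tell when the whole trial stops, or what power the planned number gives.

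**Working it through.** **1. Arithmetic of the stated counts.** 145 + 35 = 180, so 17.b is internally consistent as 145 randomised out of 180 consented. Also 320 − 180 = 140.

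**2. Inputs.**

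- From 17.b: 80% power, 49% event rate under usual care (TAU), 35% reduction, 20% dropout in both arms, exponential hazards, m = 5, ICC = 0.01.
- From item 13: half are randomised to PLF, taken as 1:1.
- Assumed, because not stated: two-sided alpha 0.05; 12 months of follow-up (item 4.f says 12–14); 49% as the cumulative risk over that period; a variance inflation factor of 1 + (5 − 1) × 0.01 = 1.04.
- Not stated: whether 35% is a risk or a hazard reduction. Both are run.

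**3. Can 145 be reproduced?** A 35% risk reduction gives 0.49 × 0.65 = 31.85% on PLF. The hazard ratio is ln(0.6815)/ln(0.51) = 0.569, and its log is −0.563.

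- *As a total, no.* The smallest total under any relative-reduction variant is 195 (one-sided, no dropout, no inflation: 79 events / 0.404). Read as an absolute 35-point drop, the inputs give only 38 to 83.
- *As a per-arm figure, yes.* A two-sided Lakatos log-rank calculation, used as a stand-in for SAS Proc Power, with 20% exponential loss gives 278. Then 278 × 1.04 = 289 in total, or 144.6 per arm.
- *Near 320.* Schoenfeld's formula needs 4 × (1.960 + 0.842)² / 0.563² = 99.04, rounded up to 100 events. Then 100 / 0.404 / 0.8 × 1.04 = 322.

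On these assumptions the protocol's inputs call for about 290 to 320 in total.

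**4. Power at each candidate total.** With 20% exponential loss (rate −ln 0.8 = 0.223), the probability of an observed event is λ/(λ + 0.223) × (1 − e^−(λ + 0.223)). This gives 0.445 for TAU and 0.287 for PLF, mean 0.366. Effective events are N × 0.366 / 1.04. Power is Φ(√events / 2 × 0.563 − 1.960). For a hazard ratio of 0.65, the mean probability is 0.382 and the log hazard ratio is −0.431.

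| Randomised | Events (35% risk reduction) | Power | Events (HR 0.65) | Power |
|---|---|---|---|---|
| 145 | 51.0 | 52% | 53.3 | 35% |
| 180 | 63.4 | 61% | 66.2 | 42% |
| 320 | 112.6 | 85% | 117.7 | 65% |

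The Lakatos method gives 51%, 60% and 84% for the risk reduction. One-sided at 0.05, the Schoenfeld figures are 64%, 72% and 91%.

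**5. Consented or randomised.** The form (section B, item 1) equates enrolled with having signed consent, so 320 may count consents. At the ratio that 17.b implies, 320 × 145/180 = 258 would be randomised. Events are then 258 × 0.366 / 1.04 = 90.8, and power is about 76% (about 55% for HR 0.65).

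**The case against.** The best defence is that this is one site's IRB form. Items 4.a and 4.b answer different prompts. Since the form treats enrolment as signing consent, item 4.a, the recruitment paragraph and 17.b agree on 180 consents, and no passage calls 145 a recruitment target. A larger total also fits the four VAs in 17.a, the work with other IRBs and the SAP's site adjustment, and it is close to what the 17.b inputs require.

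Much of this stands. Within JJPVA the consent target can be read as 180, and 320 is not implausible. But the defence leaves the trial-wide total unexplained. It does not say where the other 140 are enrolled, and it conflicts with the purpose statement, the JJPVA-only enrolment sentences and item 20.a(2).

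Two stronger readings are tempting and are not supported:

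- *The SAP's site adjustment depends on arm.* A reader might infer this because PLF groups meet on JJPVA wings, or during COVID-19 "group sessions will be held through telehealth", while Veterans referred from elsewhere might receive TAU at home. No passage codes site that way or says where those Veterans receive TAU, and in the SAP both arms receive it. Read as the enrolling or referring VA, site is fixed at baseline. If everyone is enrolled at JJPVA, it is a constant. The documents show only that the term is undefined.
- *145 is a per-arm number mistaken for a total.* The arithmetic fits, but 17.b does not say so, and alpha is assumed.

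**Conclusion.** The concern holds for trial size. The protocol describes both a trial of 180 consents enrolled at one VA and a multisite trial of 320, and 17.b sizes only the first.

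The consequence is material. Moving from 145 to 320 randomised takes power from about 52% to 85% for a 35% risk reduction, or from about 35% to 65% for a 35% hazard reduction. Only 320 randomised, with 35% read as a risk reduction, reaches the stated 80% at two-sided 0.05. If 320 counts consents, it falls slightly short on that reading.

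These figures rest on the assumed alpha, a 12-month horizon, 49% as cumulative risk over that horizon, and the simple form of the inflation factor. A one-sided test raises them but leaves 145 and 180 below 80%.

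The undefined site term is a minor gap in detail. It is not evidence of a biased analysis.

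**What to change.** 1. Recompute 17.b before choosing a total. State alpha, sidedness, follow-up and whether 35% refers to risk or hazard, and check whether 145 was a per-arm output. Do not default to 145.
2. State one trial-wide total, with consented and randomised numbers given separately, and report the power that it delivers.
3. Tie the recruitment stop in item 11 to the number randomised.
4. Make items 2, 4.a, 4.b, 11, 17.b and 20.a(2) agree on the total, the enrolling site or sites, and who may enrol. If Veterans from other VAs are eligible, item 20.a(2) must say so. If 320 is the real total, say where the other 140 are enrolled.
5. As a minor clarification in the SAP, define site as the referring or enrolling VA, fixed before randomisation, for the Cox model and all mixed models. Confirm that it is recorded, since no passage says that it is.

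The cost is one recalculation and short edits to both documents. The downside is that the stated power, or the number required, may become less favourable than the present text suggests.
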